### 10.4.2 Safety Endpoints

Safety and tolerability will be assessed by clinical review of all relevant parameters including AEs, SAEs, fatal AEs, laboratory tests, and vital signs as described in Section 9.5.

Furthermore, specific events will be collected and designated as ECIs as described in Section 9.3.7.

## **10.5 Analysis Populations**

### **10.5.1 Efficacy Analysis Populations**

The All Subjects as Treated (ASaT) population will be used for the analysis of ORR, DCR, TTR, PFS, and OS. ASaT population consists of all subjects who received at least one dose of study treatment.

The analysis population for DOR consists of responders who have best response of CR or PR in the ASaT.

### **10.5.2 Safety Analysis Populations**

The All Subjects as Treated (ASaT) population will be used for the analysis of safety data in this study.

At least one laboratory or vital sign measurement obtained subsequent to at least one dose of study treatment is required for inclusion in the analysis of each specific parameter. To assess change from baseline, a baseline measurement is also required.

## **10.6 Statistical Methods**

### **10.6.1 Statistical Methods for Efficacy Analyses**

The main analytical objective of the trial is to estimate ORR of TS-1 + oxaliplatin + pembrolizumab therapy (Cohort 1) and TS-1 + cisplatin + pembrolizumab therapy (Cohort 2) assessed by the BICR to estimate the magnitude of add-on effect of pembrolizumab co-administered with TS-1 + oxaliplatin and TS-1 + cisplatin in PD-L1 positive advanced gastric or gastroesophageal junction (GEJ) adenocarcinoma. The point estimate and 95% confidence interval will be provided using exact binomial method proposed by Clopper and Pearson (1934). Subjects in the primary analysis population (ASaT) without ORR data will be counted as non-responder.

For DOR, PFS, TTR and OS, Kaplan-Meier (KM) curves and median estimates from the KM curves will be provided as appropriate.

Censoring rules for DOR are summarized in [Table 13](#).

Table 13 Censoring Rules for DOR

Situation	Date of progression or censoring	Outcome
No progression nor death, no new anti-cancer therapy initiated	Last adequate assessment	Censor (non-event)
No progression nor death, new anti-cancer therapy initiated	Last adequate assessment before new anti-cancer therapy initiated	Censor (non-event)
Death or progression after $\geq 2$ consecutive missed adequate disease assessments	Last adequate assessment prior to $\geq 2$ missed adequate disease assessments	Censor (non-event)
Death or progression after $\leq 1$ missed adequate disease assessments	Death or progression	End of response (Event)

Patients are considered to have an ongoing response if censored, alive, have not progressed, have not started a new anti-cancer therapy and have not been determined to be lost to follow-up.

For each Cohort, the efficacy endpoints, analysis population, and statistical methods (including missing data handling) that will be employed for the efficacy analyses are presented in [Table 14](#).

Table 14 Summary of Analysis Strategy for Efficacy Endpoints

Endpoint	Statistical Method	Analysis Population	Missing data approach
Primary Endpoint			
ORR • RECIST 1.1 by BICR	Exact method based on binomial distribution	ASaT in all below populations: Cohort 1 Cohort 2	Subjects with missing data are considered non-responders
Secondary Endpoints			
ORR • iRECIST by BICR	Exact method based on binomial distribution	ASaT in all below populations: Cohort 1 Cohort 2	Subjects with missing data are considered non-responders
DCR • RECIST 1.1 by BICR • iRECIST by BICR	Exact method based on binomial distribution	ASaT in all below populations: Cohort 1 Cohort 2	Subjects with missing data are considered as disease not under control
TTR • RECIST 1.1 by BICR • iRECIST by BICR	Summary statistics using Kaplan-Meier method	ASaT in all below populations: Cohort 1 Cohort 2	Censored at last assessment date
PFS • RECIST 1.1 by BICR • iRECIST by BICR	Summary statistics using Kaplan-Meier method	ASaT in all below populations: Cohort 1 Cohort 2	Censored at last assessment date
OS			
DOR • RECIST 1.1 by BICR • iRECIST by BICR	Summary statistics using Kaplan-Meier method	Responders in below populations: Cohort 1 Cohort 2	Censored at last assessment date

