#### 10.4.1.2 Secondary Efficacy Endpoints

- Objective response rate (ORR) - per iRECIST assessed by BICR.
- Duration of Response (DOR) – per RECIST 1.1 assessed by BICR and per iRECIST assessed by BICR.

For subjects who demonstrated CR or PR, response duration is defined as the time from the date of first response (CR or PR) until the date of disease progression or death.

- Disease Control Rate (DCR): - per RECIST 1.1 assessed by BICR and per iRECIST assessed by BICR.

DCR is defined as proportion of subjects in the analysis population who have CR or PR or stable disease (SD).

- Time to Response (TTR) - per RECIST 1.1 assessed by BICR and per iRECIST assessed by BICR.

Time to response is defined as a time from the date of enrollment day to the first date of confirmed CR or PR.

- Progression-free Survival (PFS) - per RECIST 1.1 assessed by BICR and per iRECIST assessed by BICR.

PFS is defined as the time from the date of enrollment day to the first documented disease progression or death due to any cause, whichever occurs first.

- Overall survival (OS)

OS is defined as the time from the date of enrollment day to death due to any cause. Subjects without documented death at the time of the final analysis will be censored at the date of the last follow-up.

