### *Assessment and Decision at RECIST 1.1 Progression*

For participants who show evidence of radiological PD by RECIST 1.1 as determined by the investigator, the investigator will decide whether to continue a participant on study treatment until repeat imaging is obtained (using iRECIST for participant management (see Table 11 and Figure 2). This decision by the investigator should be based on the participant's overall clinical condition.

Clinical stability is defined as the following:

- Absence of symptoms and signs indicating clinically significant progression of disease
- No decline in ECOG performance status
- No requirements for intensified management, including increased analgesia, radiation, or other palliative care

Any participant deemed **clinically unstable** should be discontinued from study treatment at site-assessed first radiologic evidence of PD, and is not required to have repeat tumor imaging for confirmation of PD by iRECIST.

If the investigator decides to continue treatment, the participant may continue to receive study treatment and the tumor assessment should be repeated 4 to 8 weeks later to confirm PD by iRECIST, per investigator assessment. Images should continue to be sent in to the BICR for potential retrospective BICR.

Tumor flare may manifest as any factor causing radiographic progression per RECIST 1.1, including:

- Increase in the sum of diameters of target lesion(s) identified at baseline to  $\geq 20\%$  and  $\geq 5$  mm from nadir
  - Note: the iRECIST publication uses the terminology “sum of measurements”, but “sum of diameters” will be used in this protocol, consistent with the original RECIST 1.1 terminology.
- Unequivocal progression of non-target lesion(s) identified at baseline
- Development of new lesion(s)

iRECIST defines new response categories, including iUPD (unconfirmed progressive disease) and iCPD (confirmed progressive disease). For purposes of iRECIST assessment, the first visit showing progression according to RECIST 1.1 will be assigned a visit (overall) response of iUPD, regardless of which factors caused the progression.

At this visit, target and non-target lesions identified at baseline by RECIST 1.1 will be assessed as usual.

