### *Resolution of iUPD*

Progression is considered not confirmed, and the overall response becomes iSD/iPR/iCR, if:

- None of the progression-confirming factors identified above occurs, AND
- The target lesion sum of diameters (initial target lesions) is not above the initial PD threshold.

The response is classified as iSD or iPR (depending on the sum of diameters of the target lesions), or iCR if all lesions resolve.

In this case, the initial iUPD is considered to be pseudo-progression, and the level of suspicion for progression is “reset”. This means that the next visit that shows radiographic progression, whenever it occurs, is again classified as iUPD by iRECIST, and the confirmation process is repeated before a response of iCPD can be assigned.

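### Time to response is estimated by Kaplan-Meier in all treated subjects with non-responders censored, so one minus the curve is not the proportion who have responded

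*Combined protocol and SAP*

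**What the plan says.** Section 10.4.1.2 defines the endpoint: "Time to response is defined as a time from the date of enrollment day to the first date of confirmed CR or PR". Response is the only event named.

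Section 10.5.1 sets the population: "The All Subjects as Treated (ASaT) population will be used for the analysis of ORR, DCR, TTR, PFS, and OS". ASaT is everyone who received at least one dose, responder or not. Duration of response is treated differently in the same section: "The analysis population for DOR consists of responders who have best response of CR or PR in the ASaT".

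For the method, Section 10.6.1 says "For DOR, PFS, TTR and OS, Kaplan-Meier (KM) curves and median estimates from the KM curves will be provided as appropriate". The TTR row of Table 14 repeats this as "Summary statistics using Kaplan-Meier method" in ASaT, and its missing-data column reads "Censored at last assessment date". Table 13, which sets out events and censoring case by case, covers duration of response only. The plan has no cumulative-incidence method and no responder-only summary for TTR.

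TTR is reported by RECIST 1.1 and by iRECIST, in each of two cohorts. Under iRECIST, Appendix 2 states that "the first visit showing progression according to RECIST 1.1 will be assigned a visit (overall) response of iUPD". It also allows that status to resolve: "Progression is considered not confirmed, and the overall response becomes iSD/iPR/iCR, if" two conditions are met. The TTR rules do not distinguish the two criteria.

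**The concern.** Kaplan-Meier assumes that a censored subject would go on to have the event at the same rate as those still under observation. That is reasonable for a subject who is still on study and being scanned. It is not reasonable for one who has died, or who has progressed by RECIST 1.1 without responding. Under Section 9.2.1.2 imaging generally stops at investigator-identified progression (apart from the iRECIST option), new anticancer therapy or death. The last assessment of a non-responder is therefore usually close to the event that ended the chance of response.

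The same wording in the PFS row does no such harm, because progression and death are PFS events. In the TTR row it removes failures from the risk set and in effect redistributes them to later responders.

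Two things are at stake in the report. A TTR curve could end above the ORR shown for the same subjects, and a finite median TTR could be quoted when fewer than half respond. With two criteria and two cohorts, this can occur in up to 2 × 2 = 4 summaries.

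**Working it through.** **Inputs from the plan.** n = 40 analysed per cohort (Section 10.9); scans every 6 weeks (Section 9.2.1.2); event, population, method and censoring as set out above. The plan states no figure for TTR. The ORR used in the main example, 18/40 = 45.0%, is a row of Table 15; its exact interval (29.3 to 61.5) reproduces as 29.26 to 61.51.

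**Inputs assumed.** The documents give no response or progression times. All timings below are assumptions placed on the 6-week grid.

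**Formulas.** With d responses among r at risk at each scan, S = product of (1 - d/r), and the plan's curve is 1 - S. With no administrative censoring, the cumulative incidence of response (Aalen-Johansen) is responders to date divided by n. A non-responder whose last scan is at week t is at risk at t and removed afterwards.

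**Worked cohort, 18 of 40 respond (12/4/2 at weeks 6/12/18).** Seven non-responders have their last scan at week 6 and five at week 12.

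| Week | At risk | Responses | S | 1-KM | Cumulative incidence |
|---|---|---|---|---|---|
| 6 | 40 | 12 | 28/40 = 0.700 | 0.300 | 12/40 = 0.300 |
| 12 | 40-12-7 = 21 | 4 | 0.700 × 17/21 = 0.567 | 0.433 | 16/40 = 0.400 |
| 18 | 21-4-5 = 12 | 2 | 0.567 × 10/12 = 0.472 | 0.528 | 18/40 = 0.450 |

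1-KM passes one half at week 18, so a median of 18 weeks would be reported. The cumulative incidence never reaches one half; 22 of 40 do not respond.

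**Variants, same last-scan proportions.**
- Slower responses, 9/5/4: S = 31/40 × 19/24 × 10/14 = 0.438, so 1-KM = 56.2% against 45.0%.
- 24 responders, 17/5/2, with five and four non-responders censored after weeks 6 and 12: S = 23/40 × 13/18 × 7/9 = 0.323, so 1-KM = 67.7% against 60.0%. Both medians fall at week 12.
- All 18 responses at week 6: 1-KM = 18/40 = 45.0%, no excess.

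**Large-sample excess of 1-KM over ORR, in points.**

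| Pattern | Response times (share of responders) | Non-responders' last scans, weeks 6/12/18/24/30 | ORR 40% | ORR 45% | ORR 60% |
|---|---|---|---|---|---|
| Base | 70/20/10% at weeks 6/12/18 | 30/25/15/15/15% | 6.6 | 7.1 | 7.9 |
| Slower responses | 50/30/20% at weeks 6/12/18 | as base | 10.2 | 10.7 | 11.0 |
| Faster responses | 85/15% at weeks 6/12 | as base | 2.2 | 2.5 | 2.9 |
| Late progression | as base | 10/15/20/25/30% | 1.9 | 2.1 | 2.4 |
| Slow responses, early progression | 45/30/15/10% at weeks 6/12/18/24 | 50/25/10/10/5% | 26.8 | 27.1 | 24.6 |

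Base row at ORR 45%: S = 0.685 × (1 - 0.090/0.520) × (1 - 0.045/0.2925) = 0.479, so 1-KM = 0.521 and the excess is 7.1 points.

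**At n = 40.** In 6,000 simulated cohorts at true ORR 45% under base timings, the mean excess was 7.1 points (5th to 95th percentile 2.0 to 14.2). Among runs with observed ORR below 50%, Kaplan-Meier still gave a finite median in 40%, 60%, 11%, 7% and 95% of them, in the order of the table.

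**A second set of assumptions.** Responses fell 55/25/12/8% at weeks 6/12/18/24, with median time to progression in non-responders of 12 to 24 weeks and 2,000 runs per setting. The mean endpoint of 1-KM was 44.6% to 50.8% at true ORR 40%, and 65.4% to 71.6% at 60%. Over true ORRs of 40% to 70% the excess was about 5 to 12 points.

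**The case against.** **No rule for progression or death is stated.** The censoring phrase sits in Table 14's missing-data column, and the identical phrase in the PFS row cannot govern progression or death. That is fair: censoring these subjects is an inference. But it is the only rule given, and a Kaplan-Meier analysis of response in all treated subjects has to censor non-responders somewhere. The qualifier closing the 10.6.1 sentence names no alternative, and Table 14 repeats the method without it.

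**The plan never presents 1-KM as the response rate.** ORR is estimated separately, with missing data counted as non-response. This limits the harm, but the curve and its median would still be read as describing when the treated subjects respond, which they do not.

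**The effect on the median is narrow.** Under base timings, at ORRs of 40, 45, 50, 60, 70 and 80%, the two medians differ only at 45%. Below 50% ORR a Kaplan-Meier median appears only from about 43.5%. With faster responses or late progression they agree at all six values. This stands. With slower responses they separate more; at ORR 60% the medians are 12 and 18 weeks.

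**The sizes rest on assumed timings.** This also stands: two of the five patterns give under 3 points at each ORR tabulated. The direction of the error does not depend on them, except where the excess is nil.

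**The endpoint is descriptive, and Section 10 allows non-confirmatory analyses to be revised in the supplemental SAP.** Both are true. They make the correction easy, but they do not supply it.

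**Conclusion.** The concern holds. Followed as written, the TTR analysis treats progression and death without response as non-informative censoring. 1-KM then overstates the proportion responded whenever a non-responder is censored before the last response. Under the timings tried, the large-sample excess is about 2 to 11 points in four patterns and 25 to 27 in the most adverse. It is zero if all responses fall at week 6, or if no non-responder is censored before the last response. Every size is conditional on assumed timings; the mechanism is not.

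This is a reporting error in a descriptive secondary endpoint. The primary ORR, its exact interval and the sample size do not depend on TTR. It should be fixed before data lock because the correction is simple and the output would otherwise conflict visibly with the ORR.

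**What to change.** **Recommended change.**
- Section 10.5.1: take TTR out of the ASaT list and define its population as subjects with a confirmed response by the criterion concerned, as is already done for duration of response.
- Section 10.6.1: remove TTR from the Kaplan-Meier sentence and state that it will be summarised by median and range in confirmed responders.
- Table 14, TTR row: method, descriptive statistics (median, range); population, confirmed responders; missing data, not applicable.
- Section 10.1 lists ASaT as the efficacy population without exceptions; a short note there would keep it consistent.

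**Optional, if a curve over all treated subjects is wanted.** Use the Aalen-Johansen cumulative incidence of confirmed response, censoring only subjects still able to respond, at the last adequate assessment. The competing events are:
- RECIST 1.1: progression, death or new anticancer therapy without response.
- iRECIST: confirmed progression (iCPD, not iUPD), death or new anticancer therapy without response.

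Three details need a stated rule. One is a subject whose investigator-identified progression is not verified by central review, since TTR is by central review. Another is iUPD with no later scan, because Appendix 2 does not require repeat imaging in clinically unstable participants. The third is new therapy: Table 13 censors at it for duration of response, so counting it as a competing event here should be justified.

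**Cost.** Wording in two sections and one table row, plus the note in 10.1; no new data and no change to the primary analysis. The responder-only summary does not describe the whole cohort, so it should be shown beside the ORR. The optional curve needs a little more programming.

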## **10.6.2 Statistical Methods for Safety Analyses**

Safety and tolerability will be assessed by clinical review of all relevant parameters including adverse experiences (AEs), laboratory tests, vital signs. Count and percentage of AE will be provided.

## **10.6.3 Summaries of Baseline Characteristics, Demographics, and Other Analyses**

The number and percentage of subjects screened, enrolled, the primary reasons for screening failure, and the primary reason for discontinuation will be displayed. Demographic variables (e.g., age, gender), baseline characteristics, primary and secondary diagnoses, and prior and concomitant therapies will be summarized either by descriptive statistics or categorical tables for all enrolled subjects.

## **10.7 Interim Analyses**

No interim analysis is planned in this study.

## **10.8 Multiplicity**

No multiplicity adjustment will be applied.

## **10.9 Sample Size and Power Calculations**

A total of 80 subjects (TS-1 + oxaliplatin + pembrolizumab group [Cohort 1], 40 subjects; TS-1 + cisplatin + pembrolizumab group [Cohort 2], 40 subjects) will be included in the all participants as treated (ASaT). A total of 90 subjects (Cohort 1, 45 subjects; Cohort 2, 45 subjects) will be enrolled.

The sample size set with 90 subjects (Cohort 1 45 subjects; Cohort 2 45 subjects) that can expect a similar confidence interval of ORR to the previous studies of the first line treatment for gastric cancer for the purpose of the estimation of the ORR.

Considering approximately 10% of untreated subjects excluded, a total of 90 subjects (Cohort 1, 45 subjects; Cohort 2, 45 subjects) will be enrolled and a total of 80 subjects (Cohort 1, 40 subjects; Cohort 2, 40 subjects) will be included as ASaT.

[Table 15](#) show the two-sided 95% confidence interval of ORR when the number of subjects is 80 (40 subjects in Cohort 1 and 40 subjects in Cohort 2).

Table 15 Two sided 95% Confidence interval of ORR with 40 subjects as ASaT

Number of Observed Responders	ORR Estimates	95% CI of ORR (%)
16	40.0%	(24.9, 56.7)
17	42.5%	(27.9, 59.)
18	45.0%	(29.3, 61.5)
19	47.5%	(31.5, 63.9)
20	50.0%	(33.8, 66.2)
21	52.5%	(36.1, 68.5)
22	55.0%	(38.5, 70.7)
23	57.5%	(40.9, 73.0)
24	60.0%	(43.3, 75.1)
25	62.5%	(45.8, 77.3)
26	65.0%	(48.3, 79.4)
27	67.5%	(50.9, 81.4)
28	70.0%	(53.5, 83.4)
29	72.5%	(56.1, 85.4)
30	75.0%	(58.8, 87.3)
31	77.5%	(61.5, 89.2)
32	80.0%	(64.4, 90.9)

There will be approximately 40 subjects enrolled for each cohort, [Table 16](#) shows the two-sided 95% CI of AE rate with 40 subjects.

Table 16 Two-sided 95% CI of AE incidence rate with 40 Subjects

Number of AE	AE incidence rate estimates	95% CI of incidence rate (%)
1	2.5%	(0.00, 13.2)
2	5.0%	(0.61, 16.9)
3	7.5%	(1.57, 20.4)
4	10.0%	(2.8, 23.7)
5	12.5%	(4.2, 26.8)
6	15.0%	(5.7, 29.8)
7	17.5%	(7.3, 32.8)
8	20.0%	(9.1, 35.7)
9	22.5%	(10.8, 38.5)

Number of AE	AE incidence rate estimates	95% CI of incidence rate (%)
10	25.0%	(12.7, 41.2)
11	27.5%	(14.6, 43.9)
12	30.0%	(16.6, 46.5)
13	32.5%	(18.6, 49.1)
14	35.0%	(20.6, 51.7)
15	37.5%	(22.7, 54.2)

### 10.10 Subgroup Analyses and Effect of Baseline Factors

The estimate of the treatment effect for the primary endpoint will be estimated and/or plotted within each category of selected factors (e.g., analyses for each patient background factors). The details will be described in the sSAP.

### 10.11 Compliance (Medication Adherence)

Drug accountability data for study treatment will be collected during the study. Any deviation from protocol-directed administration will be reported.

### 10.12 Extent of Exposure

Extent of Exposure for a subject is defined as number of cycles in which the subject receives the study medication infusion. Summary statistics will be provided on Extent of Exposure for ASaT population.

## 12. Appendices

### 12.1 Appendix 1: Study Governance Considerations

#### Merck Code of Conduct for Clinical Trials

**Merck\***  
**Code of Conduct for Clinical Trials**

#### **I. Introduction**

##### **A. Purpose**

Merck, through its subsidiaries, conducts clinical trials worldwide to evaluate the safety and effectiveness of our products. As such, we are committed to designing, implementing, conducting, analyzing and reporting these trials in compliance with the highest ethical and scientific standards. Protection of participant safety is the overriding concern in the design of clinical trials. In all cases, Merck clinical trials will be conducted in compliance with local and/or national regulations and in accordance with the ethical principles that have their origin in the Declaration of Helsinki.

##### **B. Scope**

Such standards shall be endorsed for all clinical interventional investigations sponsored by Merck irrespective of the party (parties) employed for their execution (eg, contract research organizations, collaborative research efforts). This Code is not intended to apply to trials which are observational in nature, or which are retrospective. Further, this Code does not apply to investigator-initiated trials which are not under the control of Merck.

